Population: The study population will include individuals with SCD between 12 and 85 years of age who are enrolled in a health insurance plan (commercial, Medicare, Medicaid) continuously during the 365 days prior to and including the index date (baseline) and 180 days post-index. The index selection period will be November 25, 2019 (date of FDA accelerated approval for voxelotor) through January 31, 2023. The exposed group will include patients with a new prescription claim for voxelotor (no use 365 days prior), while the control group will include matched patients who do not have a prescription claim for voxelotor. The exposed group will index on the voxelotor prescription claim date and will be sequentially coarsened-exact-matched with up to four non-voxelotor patients based on age and calendar date. Both the exposed and control groups may be treated with other standard of care (SOC) treatments, such as hydroxyurea, during the study period.

Variables: The exposure of interest will be a voxelotor prescription claim. Baseline characteristics and covariates for PS modeling will include demographic information (e.g., age, sex, insurance type) as well as patient characteristics (e.g., specialty provider type, common SCD comorbidities, treatment history, Hb levels, number of prior RBC transfusions, and healthcare utilization). The primary outcome of interest is RBC transfusion. Exploratory outcomes include VOC, stroke, and RBC transfusion complications. Tables 4 and 5 define exposures, outcomes, and key covariates.

Data sources: The study will use the Komodo Healthcare Map (KHM) database linked to Claritas prescription data (proprietary voxelotor claims) and Quest Diagnostics lab data. Data sources are anchored on a closed system of administrative claims, including patient enrollment, physician, facility, and pharmacy claims.

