9.2. Setting

The study population will include US patients with SCD between the ages of 12 and 85 years who are enrolled in a health insurance plan (commercial, Medicare, Medicaid) continuously during the 365 days prior to and including the index date (baseline) and 180 days post-index. The index selection period is November 25, 2019 (date of Food and Drug Administration [FDA] accelerated approval for voxelotor) through January 31, 2023. The exposed group will include patients with a new prescription claim for voxelotor (no prior use 365 days prior to index date), while the control group will include matched patients who do not have a prescription claim for voxelotor. Non-voxelotor controls will include those receiving no SCD-modifying therapies as well as those receiving non-voxelotor SCD treatments to be reflective of clinical practice. Patients who have a history of stroke will be excluded from this analysis. Both the exposed and control groups may be treated with other SOC treatments such as HU and have 2 or more documented RBC transfusions prior to study index.

Depending on the source of information, approximately 50% of individuals with SCD in the US have received a RBC transfusion, and approximately 20% have received a transfusion in the past year. ¹⁶ In the feasibility assessment of Komodo Healthcare Map (KHM) dataset, race/ethnicity was documented for 90% (n=2230/2486) of patients with 87% (n=1929/2230) identifying as Black or African American. The Centers for Disease Control and Prevention (CDC) estimates 90% of individuals with SCD in the US are non-Hispanic Black or African American. ¹⁷ Socioeconomic status also plays an important factor in impacting patient behavior and access to care. While the KHM dataset does not have direct measures of patients' socioeconomic status, important indicators will be leveraged in the analysis for patients including geography by region, health insurance type, and whether a hematologist is involved in the patient's care. KHM is nationally representative of individuals with SCD. In the Komodo data, approximately 68% of patients have Medicaid as their primary insurance type.

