Region	Baseline Characteristic; Covariate	[Index]	Frequency and proportion (N, %) Categorical: Northeast, Midwest, South, and West Regions (based on Census geographic regions), Missing
Top 10 Diagnosing Provider Specialty	Baseline Characteristic; Covariate	[Baseline]	Frequency and proportion (N, %) [Provider specialty categories will be included in statistical analysis plan (SAP)]
SCD Hematology Diagnosing Provider	Baseline Characteristic; Covariate	[Baseline]	Frequency and proportion (N, %) Binary: Yes, No (including non-hematology and null values)
SCD Genotype ¹	Baseline Characteristic	[Baseline]	Frequency and proportion (N, %) Categorical: Homozygous SS, HbSC, HbSB0 thalassemia, HbSB+ thalassemia, Unknown, Multiple genotypes reported
Comorbidities – SCD specific morbidities ²	Baseline Characteristic; Covariate	[Baseline]	Frequency and proportion (N, %)
Hydroxyurea	Baseline Characteristic; Covariate	[Baseline]; [Follow- up]	Frequency and proportion (N, %)
Crizanlizumab	Baseline Characteristic; Covariate	[Baseline]; [Follow- up]	Frequency and proportion (N, %)
L-glutamine	Baseline Characteristic; Covariate	[Baseline]; [Follow- up]	Frequency and proportion (N, %)
Erythropoietin Stimulating Agent (ESA)	Baseline Characteristic; Covariate	[Baseline]; [Follow- up]	Frequency and proportion (N, %)

V2.0 23 December 2024			
RBC transfusion	Baseline Characteristic; Covariate	[Baseline]; [Follow-up]	Continuous: Mean (SD); Median (IQR); Minimum; Maximum.
Baseline Hb lab test	Baseline Characteristic	[Baseline]	Frequency and proportion (N, %) Categorical: Komodo lab test only, Quest lab test only, Komodo lab test and Quest lab test, No value
Baseline Hb value ³	Baseline Characteristic	[Baseline]	Continuous: Mean (SD); Median (IQR); Minimum; Maximum.
Charlson Comorbidity Index (CCI) ⁴	Baseline Characteristic; Covariate	[Baseline]	Continuous: Mean (SD); Median (IQR); Minimum; Maximum. Frequency and proportion (N, %) For individual categories see SAP.
Healthcare Interactions - Inpatient/Outpatient Visit	Baseline Characteristic; Covariate	[Baseline]	Continuous: Mean (SD); Median (IQR); Minimum; Maximum.
Follow-up time	Baseline Characteristic; Covariate	[Follow-up]	Continuous: Mean (SD); Median (IQR); Minimum; Maximum.
Voxelotor	Exposure	[Index]; [Follow-up]	Frequency and proportion (N, %)
Iron overload	Baseline Characteristic; Covariate	[Baseline]	Frequency and proportion (N, %)

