Required 1-year minimum follow-up	Two subgroup analyses have been proposed to evaluate bias introduced by differential follow-up. First, a subgroup analysis of patients with a minimum of 1-year of follow-up will be performed to evaluate the impact of informative censoring.	To address the impact of informative censoring and differential follow-up
Matched censoring	If meaningful differences in follow-up time are observed, matched censoring will be performed to assess the impact of differential follow-up between the exposed and referent group for the primary objective. Bias due to differential follow-up can arise when the reasons for participants dropping out or being lost to follow-up are related to both the treatment and the outcome. Matched censoring mitigates this bias by censoring all patients within a matched set (i.e., patients that have been matched by PS matching) at the earliest time in which a patient in the set was censored. In the context of 1:2 PS matching, where each exposed patient is matched to two referent patients, the matched set will consist of at most three individuals. Thus, matched censoring in this scenario involves censoring data for all three individuals in a matched set at the earliest observed censoring time among them.	To address the impact of informative censoring and differential follow-up
Stratification by number of RBC transfusions in baseline	The number of RBC transfusions PPPY in baseline will be categorized and the primary objective will be reported separately for those categories. This analysis will be performed for all objectives.	To understand the effect of the treatment on high-risk subgroups.
Subgroup analysis by Hb level	The primary analysis will also be performed on a subgroup of patients with Hb values at baseline. A separate PS model will be utilized for this subgroup.	To understand the effect of the treatment on high-risk subgroups and patients with available baseline data.
Subgroup analysis by prior medications	A subgroup analysis will be performed on patients who received hydroxyurea, crizanlizumab, L-glutamine, and/or ESA in baseline the exposed and referent groups.	To understand the effect of other SCD treatments.

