Subgroup analysis by concomitant medications	A subgroup analysis will be performed on patients who received hydroxyurea, crizanlizumab, L-glutamine, and/or ESA in baseline the exposed and referent groups. This subgroup analysis will be performed for the Primary Objective and the Exploratory Objective 1 (VOCs).	To understand the effect of other SCD treatments.

Abbreviations: ITT: Intention-to-treat; PPPY: per patient per year; SCD: Sickle cell disease

All subgroup analyses and stratifications must meet a minimum sample size criteria in each group to be performed (see SAP for more detail). Exploratory objective 1 which evaluates the change in the rate of VOCs and its separate components from baseline through follow-up will also include a sensitivity analysis utilizing alternative definitions for VOCs, given a higher likelihood of misclassification in claims using ICD-10 codes alone; these alternative VOC definitions will be detailed in code lists provided in the SAP. Other sensitivity analyses such as e-values may be considered if other possible confounders or sources of bias are identified, depending on effect size in the primary outcome or differences in baseline characteristics and/or follow-up time between the exposed and matched controls. Details on potential sensitivity analyses will be included in the SAP.

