Because this study does not include an active comparator as a control group, CEM will be used to select the index date of matched controls on the initiation of voxelotor for exposed patients. All exposed patients will be selected prior to controls to preserve sample size. Sampling bias may be introduced by prioritizing exposures, but the impact is limited due to a larger pool of untreated control patients than potential exposures. There may be differences in patient characteristics dependent on when patients enter the study population (i.e., initiating voxelotor versus periods without treatment for matched controls). However, PS methods will be utilized to control for observed baseline confounding between the exposed and referent groups. Linked Ouest data will be used to evaluate Hb levels in baseline (an important diagnostic criterion for RBC transfusions). Feasibility analyses will be conducted prior to implementation to assess the number of patients in this study with available Hb data. Assuming a significant number of patients will not have Hb data in baseline, a sensitivity analysis has been proposed to assess the primary outcome among patients with this lab data. However, there may be differences in the frequency of Hb testing between the exposed and control group, relative to when patients enter the study cohort. For most subgroup analyses, the PS obtained from the overall study cohort PS model will be used for PS adjustment. However, for the subgroup of patients with non-missing Hb values in baseline, the PS model will be re-fit and will include an additional covariate (mean Hb value). Depending on the utilization of other SOC treatments in both the exposed and control groups, other subgroup analyses may be conducted. Additionally, the primary analysis will be as-treated, which includes discontinuation of voxelotor as a censoring criterion in the exposed group. This creates potential for confounding via differential censoring between the exposed and referent groups. However, to account for these potential differences in follow-up time, matched censoring will be used to censor matched controls on the date of their voxelotor match's discontinuation date as a sensitivity analysis.

A summary of the potential limitations of the RWD in this study and the mitigation strategies that will be applied is provided in Annex Table 3.

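### Table 7 defines the concomitant-medications subgroup by baseline use, so it duplicates the prior-medications subgroup for the primary endpoint and mislabels the VOC analysis

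*Protocol*

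**What the plan says.** Table 7 in Protocol Section 9.7.3 has two adjacent rows on other sickle cell treatments. The first reads, in part: "Subgroup analysis by prior medications A subgroup analysis will be performed on patients who received hydroxyurea, crizanlizumab, L-glutamine, and/or ESA in baseline the exposed and". The second, headed as concomitant medications, opens with the same sentence, "A subgroup analysis will be performed on patients who received hydroxyurea, crizanlizumab, L-glutamine, and/or ESA in baseline the exposed and referent groups", and then adds "This subgroup analysis will be performed for the Primary Objective and the Exploratory Objective 1 (VOCs"). Both rows give the same rationale: "To understand the effect of other SCD treatments".

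Section 9.2 fixes the baseline period through the enrolment requirement, "continuously during the 365 days prior to and including the index date (baseline) and 180 days post-index". Figure 1 uses the same window for covariates and starts outcome assessment on day 1.

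Other treatment after index is expected. The abstract says "Both the exposed and control groups may be treated with other standard of care (SOC) treatments, such as hydroxyurea, during the study period". Table 4 in Section 9.3 records the four drugs in both periods; the hydroxyurea row, for example, is "Hydroxyurea Baseline Characteristic; Covariate [Baseline]; [Follow- up] Frequency and proportion (N", %). Section 9.9 adds: "Depending on the utilization of other SOC treatments in both the exposed and control groups, other subgroup analyses may be conducted".

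**The concern.** A row labelled concomitant should tell the reader how voxelotor compares with no voxelotor among patients who are also taking another sickle cell drug. Defined by any use in the 365 days up to index, it cannot do that. A patient whose last hydroxyurea fill was 11 months before index counts as a concomitant user, while a patient who starts hydroxyurea after index does not.

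Two things are at stake. First, for the primary endpoint the report would carry two labels over one estimate, and a reader could take the agreement as evidence that the result holds for both prior and concurrent use. Second, concurrent treatment matters for this outcome. Annex Table 3 names hydroxyurea as a known confounder that lowers the proportion of patients transfused, and its mitigation refers only to prior exposure. The censoring rules in Section 9.7.3 end follow-up when voxelotor is stopped, but not when hydroxyurea, crizanlizumab, L-glutamine or ESA is started or stopped. The concomitant row is therefore the one firmly planned comparative analysis whose name addresses this question, and its definition does not.

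**Working it through.** No sample size, power or event count enters this point, so there is no figure of the plan to reproduce. The check is a comparison of text.

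1. **The two rows side by side.**

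| Element | Prior-medications row | Concomitant-medications row |
|---|---|---|
| Drugs | hydroxyurea, crizanlizumab, L-glutamine, ESA | the same four |
| Exposure window | baseline | baseline |
| Rationale | effect of other SCD treatments | the same |
| Objectives | none named | primary objective and Exploratory Objective 1 (VOCs) |

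 A string comparison confirms that the 22-word defining sentence of the first row is identical to the opening sentence of the second. The only text left over in the second row names the objectives and does not alter who is selected.

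2. **Patients selected.** Same drugs and same window give the same set, so the two subgroups overlap by 100%.

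3. **Propensity score.** Section 9.9 says the overall-cohort score is used for most subgroups and names only the haemoglobin subgroup as having its own model. Nothing there separates the two medication rows.

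4. **Endpoints.** The introduction to Table 7 applies its analyses to the primary endpoint by default. The prior row names no other endpoint, so it covers the primary endpoint only. The concomitant row covers the primary endpoint and VOCs. It follows that:
 - primary endpoint: same patients, same score, same outcome, hence the same estimate twice;
 - VOCs: one analysis, found only in the concomitant row, run on baseline users.

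5. **Other places where concurrent use might be analysed.** Table 4 plans a frequency and proportion of follow-up use, which is descriptive. Section 9.9 allows further subgroups without requiring or defining any. Annex Table 3 stratifies by prior exposure. Section 9.1 says the propensity score will adjust for concurrent medications, but the covariate window in Figure 1 closes at index. None of these is a specified comparison by concurrent use.

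**The case against.** The best reply is that this is a copied sentence in one secondary subgroup row. That row runs only if a size threshold is met, and it leaves the primary population, estimate and power untouched. A second analyst must check every cohort and table under Section 9.8.1, and two rows with equal counts and equal estimates would show themselves as duplicates. Section 9.7 lets the SAP modify the plan, and the SAP is not at hand. Section 9.1 also speaks of concurrent medications where it means a baseline-measured adjustment, so the sponsor's meaning of concomitant is not certain.

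Much of this limits the point without removing it. The protocol does not leave this definition to the SAP: it states one, and the one stated contradicts its label. Section 9.8.1 also commits to following the protocol strictly, so quality control against the protocol would confirm the duplicate cohort as correct.

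Two stronger readings are tempting, and the documents do not support them. A reader might infer that the concomitant row adds nothing for VOCs either. It does add something, because the prior row does not cover VOCs; that analysis is mislabelled, not redundant. A reader might also infer that concurrent treatment is ignored altogether. Table 4 describes follow-up use, and Section 9.9 leaves room for optional subgroups. What is missing is a firmly specified comparative analysis.

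**Conclusion.** The point holds. In Table 7 the label and the operational definition of the concomitant-medications subgroup contradict each other. The patient sets of the two rows are identical. The duplication of results is complete for the primary endpoint and absent for VOCs, where the fault is the label alone. No firmly specified comparative analysis in the protocol addresses concurrent treatment.

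This rests on reading baseline as the protocol defines it, and on both rows using the overall propensity score as Section 9.9 indicates. The SAP may define the row differently; the protocol text would still need correction. The main result of the study does not depend on this row, so the point is one that should be corrected before the subgroup results are run or reported, not one that threatens the primary analysis.

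**What to change.** Change the exposure window in the concomitant row of Table 7 so that it matches the label, and keep the prior-medications row as it is. Either of two definitions would do:

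- **Use covering the index date (preferred).** For pharmacy claims, require that days' supply spans the index date. For crizanlizumab and ESA, which Annex Table 1 also identifies by procedure codes, state a look-back interval within which an administration counts as current. This separates current from past users and does not select on post-index behaviour. It does not capture patients who start one of these drugs after index.
- **Use during follow-up.** If this is what is meant, define the row on the follow-up variables already listed in Table 4, and label the result as conditioning on treatment received after index.

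The change is a sentence in Table 7 plus a short coverage definition for the procedure-coded drugs. With the preferred definition, patients covered at index would normally have a claim in the preceding 365 days, so the subgroup is largely nested in the prior-use subgroup. It will be smaller and may miss the size threshold set for subgroup analyses. The primary estimate does not change.

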9.8. Quality Control

9.8.1. Analytic Quality Control

Aetion will build measures for cohort identification, outcomes, and other variables of interest based on codes and algorithms described in this protocol. All measures created will undergo quality control review by at least one additional analyst or scientist under the supervision of the Study Lead.

This protocol will be strictly followed when conducting the analysis of this study. All cohorts developed, statistical analyses implemented, and tables completed will undergo quality control review by at least one additional analyst or scientist under the supervision of the Study Lead.

The Study Lead will review all results tables and other final deliverables to confirm accuracy, logical flow, and appropriate format.

This secondary data collection study follows the Guidelines for Good Epidemiologic Practice laid out in 2005 FDA Good Pharmacoepidemiology Practices (GPP), Best Practices for Conducting and Reporting Pharmacoepidemiologic Safety Studies Using Electronic Healthcare Data Sets and the 2015 International Society of Pharmacoepidemiology GPP. 39–41

The AEP maintains a date / time-stamped record of all analytic cohorts and corresponding analyses. 42

9.8.2. Data Storage

Aetion may retain raw and transformed data for as long as it is permitted by the data vendor. Once a contract expires that is no longer planned for renewal, Aetion will remove and destroy all raw and transformed data from Amazing Web Services (AWS) S3 as well as the Substantiate platform. Results can be downloaded from the platform and saved at any time. Results can remain on platform as long as the client has an active Substantiate license.

9.9. Strengths and limitations of the research methods

There are some distinct differences between RWE and RCT settings. RWD allows for more generalizable patient populations, but there is less standardization and higher potential for missing values for important patient characteristics (e.g., Hb levels, SCD genotype, comorbidity scores, etc.). Additionally, in an RCT environment, healthcare interactions are on a protocolized schedule for enrolled patients. In RWD, differences exist in how often a patient sees a provider and the type of provider both across groups and within groups, which is why both of these elements will be important for PS modeling. RWD allows for less restrictive inclusion/exclusion criteria and will allow for patients with more severe SCD to be evaluated; for example, all individuals with SCD and recent history of RBC transfusion are excluded from voxelotor clinical trials as well as other medications in development for SCD.

Although there are many benefits to utilizing RWD, there are some inherent limitations. Claims data sources are subject to potential misclassification of the outcome, exposure, or covariates in observational studies (i.e., the presence of a diagnosis code on a medical claim or a generic medication on a prescription claim does not indicate the presence of disease or compliance to treatment given rule out diagnosis or coding errors). 44 The extent of miscoding is believed to be small, as study variables are drawn directly from medical claims that are used for clinical documentation and insurance reimbursement. 44 Additionally, as determined through exploratory analyses, a small proportion of patients have available lab data after linking across all three data sources; Hb will also be excluded from the PS model but will have a separate subgroup analysis because it may be an important confounder in this study. Patients will be excluded from the analysis if they have evidence of stroke in baseline so that patients receiving chronic transfusions for secondary stroke prevention are not included in the analysis. Although patients may also receive transfusions for primary stroke prevention, claims data will not have information on transcranial doppler velocity, and thus such patients will not be identifiable. However, this is estimated to be a small portion of patients within the study (less than 5% of pediatric patients with SCD receive chronic transfusions). 45

When possible, validated claims-based algorithms will be utilized to define inclusion/exclusion criteria and outcomes. Pfizer conducted a validation study to assess the accuracy of medical claims billed for RBC transfusions. VOCs are more likely to be misclassified and underestimated in claims data, as only more severe VOC will be captured through claims, and there are a variety of claims-based algorithms in similar research studies. Clinical advisors (3 external hematologists) were consulted on how to best capture VOCs using medical claims, and sensitivity analyses will be conducted by using both a specific and broader algorithm informed by clinical feedback. Furthermore, a literature review was conducted to evaluate the validity of RBC transfusion procedures in both claims and EHR databases. A high positive predictive value (PPV) was found in multiple studies including both US and non-US data validating RBC transfusion procedures in claims or EHR against blood bank data. Additionally, this analysis defines a RBC transfusion as at most one transfusion per day because the data does not allow us to distinguish between the claims for

transfusions billed as multiple units or multiple procedures. As a result, we may be undercounting the true number of transfusions patients receive. However, units of blood are not well captured in claims or EHR and will be a limitation of this analysis. Furthermore, if patients receive a transfusion outside of the KHM data contributors, it will not be captured but is assumed to impact both the exposed and control groups equally.

Unmeasured confounding leading to an unobservable imbalance between the voxelotor, and referent groups may be present given not all demographic or clinical characteristics are available in the KHM database (e.g., race or ethnicity, provider characteristics, genotypes, etc.). The study population will consist of voxelotor patients who are able to be linked to proprietary claims and with standardized fields for demographic variables that may not be as generalizable (e.g., specific race or ethnic populations like 'Middle Eastern' are not reflected in claims). The COVID-19 pandemic will overlap with the study period, however, the impact on healthcare utilization is expected to be equal among the exposed and control groups. Adherence to voxelotor will be assumed with each prescription fill per the days supply. If patients are not adherent to daily doses of voxelotor, the treatment effect may be underestimated in the exposed population. However, these limitations are inherent to the data source and thus cannot be addressed in this study.

Because this study does not include an active comparator as a control group, CEM will be used to select the index date of matched controls on the initiation of voxelotor for exposed patients. All exposed patients will be selected prior to controls to preserve sample size. Sampling bias may be introduced by prioritizing exposures, but the impact is limited due to a larger pool of untreated control patients than potential exposures. There may be differences in patient characteristics dependent on when patients enter the study population (i.e., initiating voxelotor versus periods without treatment for matched controls). However, PS methods will be utilized to control for observed baseline confounding between the exposed and referent groups. Linked Ouest data will be used to evaluate Hb levels in baseline (an important diagnostic criterion for RBC transfusions). Feasibility analyses will be conducted prior to implementation to assess the number of patients in this study with available Hb data. Assuming a significant number of patients will not have Hb data in baseline, a sensitivity analysis has been proposed to assess the primary outcome among patients with this lab data. However, there may be differences in the frequency of Hb testing between the exposed and control group, relative to when patients enter the study cohort. For most subgroup analyses, the PS obtained from the overall study cohort PS model will be used for PS adjustment. However, for the subgroup of patients with non-missing Hb values in baseline, the PS model will be re-fit and will include an additional covariate (mean Hb value). Depending on the utilization of other SOC treatments in both the exposed and control groups, other subgroup analyses may be conducted. Additionally, the primary analysis will be as-treated, which includes discontinuation of voxelotor as a censoring criterion in the exposed group. This creates potential for confounding via differential censoring between the exposed and referent groups. However, to account for these potential differences in follow-up time, matched censoring will be used to censor matched controls on the date of their voxelotor match's discontinuation date as a sensitivity analysis.

A summary of the potential limitations of the RWD in this study and the mitigation strategies that will be applied is provided in Annex Table 3.

